- ^d Visit 5 Week 8 and Visit 7 Week 16 will be remote visits. Central laboratory tests, target physical examination, vital sign and weight will not be performed during these remote visits. However, if laboratory tests and/or physical examination is needed based on the Investigator's clinical judgement, an unscheduled visit should be performed at the investigational site. Urine pregnancy test kits will be provided to the subjects at Visit 4 Week 4 and Visit 6 Week 12. At Visit 5 Week 8 and Visit 7 Week 16 subjects will perform urine β -hCG test at home. IP will be dispensed at Visit 4/Week 4 and Visit 6/Week 12 for these 2 visits.
- ^e Urine pregnancy test will be performed to assess subject eligibility prior to the first administration of IP if a serum pregnancy test was not obtained within 72 hours prior to dosing (negative results required for IP administration).
- ^f Subjects who do not have a historical biopsy will undergo a liver biopsy procedure for study eligibility. The independent histopathologists will review the liver biopsy specimens to assess whether the subject meets the histological inclusion criteria. Screening liver biopsy will serve as the Baseline assessment. Subjects who discontinue after Week 20 and before Week 52 will undergo a liver biopsy procedure at ET Visit. IP should be stopped 7-10 days prior to Week 53 or ET Visit biopsy and restarted 7 days after biopsy at Week 54 if subjects participate in the active treatment phase.

^j First dose of IP should be administered at the investigative site.

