Unscheduled visits, if needed, may occur at any time, in particular for safety reasons (or efficacy reasons) as deemed necessary by the Investigator or site staff, or for any reason that the subject must return to study center as it pertains to the study (eg, to pick up additional or replacement IP). The Unscheduled Visit eCRF will be made available to the site staff, in order to record the necessary unscheduled assessments and/or procedures.

6.3. **Early Termination**

An early termination (ET) evaluation will be performed for subjects who are withdrawn from treatment for any reason as soon as possible after the decision to permanently discontinue treatment has been made.

The following evaluations will be performed as specified in the Table of Events, [Table 3](#):

- Adverse event evaluation
- Concomitant medications evaluation
- Concomitant procedures evaluation
- Counseling about pregnancy precautions and the potential risks of fetal exposure
- Complete physical examination (Section [6.5.1](#))
- Vital signs and weight (Section [6.1](#))
- 12-lead ECG (Section [6.5.2](#))
- Clinical Laboratory Evaluations (Section [6.5.3](#)):
 - Hematology panel
 - Coagulation tests
 - Chemistry panel
 - Urinalysis and urine cytology
 - Serum pregnancy test
 - Fecal occult blood test (FOBT)
- Efficacy assessment (Section [6.6](#)):
 - Liver biopsy/histology

- Investigational product (IP) return (all used and unused blister cards) and IP compliance assessment (Section 7.6)

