6.5.3. Clinical Laboratory Assessments

Clinical laboratory evaluations will be performed by a central laboratory to include the following laboratory assessments performed at the frequency specified in Table 3. Clinical laboratory evaluations are required to be fasting at Baseline Visit, Week 24 Visit, and Week 52 Visit/ Week 102 Visit (as applicable) or at the Early Termination Visit if subjects discontinue from the study prior Week 52 Visit/ Week 102 Visit (as applicable). "Abnormal, clinically significant" results should be recorded in the Medical History eCRF if found prior to first dose of IP, or in the AE eCRF if found after the first dose of IP.

- Hematology Panel: including complete blood count (CBC) with differential, including red blood cell (RBC) count, hemoglobin, hematocrit, mean corpuscular volume, mean corpuscular hemoglobin, mean corpuscular hemoglobin concentration, white blood cell (WBC) count (with differential), neutrophil count (percent and absolute), and platelet count.
- Coagulation tests: including prothrombin time (PT) and INR.
- Chemistry Panel: including total protein, albumin, calcium, phosphorous, glucose, lipid panel (total cholesterol, HDL, LDL, and triglycerides), uric acid, TBL, ALP, AST/ serum glutamic oxaloacetic transaminase (SGOT), ALT/ serum glutamic pyruvic transaminase (SGPT), sodium, potassium, chloride, carbon dioxide, blood urea nitrogen (BUN), creatinine, and lactic dehydrogenase (LDH).
- Urinalysis: including dipstick urinalysis (specific gravity, pH, glucose, ketones, protein, blood, bilirubin, leukocyte esterase, nitrite, and urobilinogen). Microscopic urinalysis (epithelial cells, RBC, WBC, and casts) will be performed only if the dipstick urinalysis is abnormal.

In addition to the routine urinalysis, urine cytology will be done for the detection of abnormal cells. The urine cytology specimen will be evaluated by a pathologist at the central laboratory.

- Mycobacterium tuberculosis (TB) testing: Testing will be done at the Screening Visit via QuantiFERON®-TB Gold.

Note: A positive QuantiFERONTB Gold test or 2 successive indeterminate QuantiFERON-TB Gold tests will disqualify the subject from further participation in the study.

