Elevated ALT and/or AST at baseline:	ALT or AST > 2 x BLM or TBL > 1.5 x BLM	Repeat ALT and AST within 48-72 hours. If elevations persist, evaluate other cause ^a of AST, ALT and TBL elevation. If the etiology is unknown, close monitoring required on a weekly basis until ALT or AST ≤ 2 x BLM and TBL ≤ 1.5 x BLM or meet the criteria for discontinuation. Subjects (whether discontinued or not) are to be followed until the laboratory value returned to baseline.
	ALT or AST > 2 x BLM and (TBL > 2 x BLM or INR increased by > 0.2 from Baseline)	Discontinue IP and follow-up signs or symptoms until resolution.
	with appearance of fatigue, nausea, vomiting, right upper quadrant pain or tenderness, fever, and rash, with or without eosinophilia (> 5%) during study	Temporarily interrupt or discontinue IP and follow-up signs or symptoms until resolution.
Elevated ALT and/or AST at baseline and BLM ^b < 2 x ULN	ALT or AST > 5 x BLM	Discontinue IP and follow-up signs or symptoms until resolution.
Elevated ALT and/or AST at baseline and BLM ≥ 2 x ULN but < 5 x ULN:	ALT or AST > 3 x BLM	Discontinue IP and follow-up signs or symptoms until resolution.

Abbreviations: ALP = alkaline phosphatase; ALT = alanine aminotransferase; AST = aspartate aminotransferase; BLM = baseline measurement(s); IP = investigational product; INR = international normalized ratio; TBL = total bilirubin; ULN = upper limit of normal.

^a Tests for causes of increases AST or ALT include infectious (Hepatitis A, Hepatitis B, Hepatitis C, Hepatitis E), acetaminophen level, toxicology screen, autoimmune (antinuclear antibodies, anti-smooth muscle antibodies, anti-liver/kidney microsomal antibodies type 1, immunoglobulin G [IgG]). Additional tests and evaluations may be requested by the medical monitor. Tests of function include serum albumin and prothrombin time (PT)/INR.

^b In subjects with screening TBL or AST or ALT, greater than 3 X ULN, baseline values should be established by at least two measurements obtained at least 4 weeks apart.

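### Appendix C, elevated ALT/AST at baseline: a bilirubin rise alone opens the monitoring row, but the 48-72 hour repeat names only ALT and AST

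*Combined protocol and SAP*

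**What the plan says.** Appendix C sets separate liver-monitoring rules by baseline aminotransferase status. For subjects with elevated ALT and/or AST at baseline, the first row has these parts:

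- Trigger: "ALT or AST > 2 x BLM or TBL > 1.5 x BLM", where BLM is the baseline measurement.
- First action and the condition that follows it: "Repeat ALT and AST within 48-72 hours. If elevations persist, evaluate other cause ^a of AST, ALT and TBL elevation".
- Continued checks, where no cause has been found: "close monitoring required on a weekly basis until ALT or AST ≤ 2 x BLM and TBL ≤ 1.5 x BLM"; they also end once a stopping rule is met.
- Closing duty: "Subjects (whether discontinued or not) are to be followed until the laboratory value returned to baseline".

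The row does not call for interrupting investigational product. The discontinuation row for the same subjects is "ALT or AST > 2 x BLM and (TBL > 2 x BLM or INR increased by > 0.2 from Baseline", with the bracket closing after the INR term.

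Section 6.5.4 refers to Appendix C for the monitoring rules and adds no retest of its own. Section 6.5.3 puts TBL, ALP, AST and ALT in one chemistry panel and lists PT and INR separately as coagulation tests. Table 3 schedules that panel at the on-site visits. Its footnote d makes Weeks 8 and 16 remote: "Central laboratory tests, target physical examination, vital sign and weight will not be performed during these remote visits".

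**The concern.** The trigger terms are joined by *or*, so a subject with ALT and AST at baseline and TBL above 1.5 x BLM enters the row. The only step with a deadline then measures two analytes that did not trigger it and does not name the one that did.

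This matters because persistence controls the next steps. Read literally, a site would receive unchanged ALT and AST at 48-72 hours and could conclude that no elevation persists. It would then start neither the work-up nor the weekly checks, and dosing would continue. What is at stake is the timing of confirmation for an isolated bilirubin rise in a population with existing liver disease. Follow-up as such is not missing, because the cell's last sentence requires it.

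**Working it through.** There is no plan figure to reproduce. The check compares the steps of the row, searches for a retest rule elsewhere, and then works out the scheduled-visit fallback.

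**1. The row, step by step (Appendix C)**

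| Step | ALT/AST named | TBL named |
|---|---|---|
| Trigger | yes | yes, sufficient alone |
| Repeat at 48-72 hours | yes | **no** |
| Cause work-up | yes | yes |
| Exit from weekly monitoring | yes | yes |

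TBL is missing only from the confirmation step. In the normal-baseline row the same repeat sentence fits, because that row is entered only on an ALT or AST elevation, with TBL below 2 x ULN. In the elevated-baseline row the trigger is wider but the repeat is not.

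**2. Is a dated TBL retest ordered anywhere else?**

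- Section 6.5.4 defers to Appendix C.
- Section 6.1 requires a second TBL when the value is abnormal, but only at screening.
- Section 6.2.1 leaves extra visits to local judgement: "Unscheduled visits, if needed, may occur at any time, in particular for safety reasons (or efficacy reasons) as deemed necessary by the Investigator". This route is therefore discretionary.
- Appendix C, footnote a, lists tests for causes of raised AST or ALT and lets the medical monitor ask for more. This is also discretionary.
- Weekly monitoring would capture TBL, but it starts only after persistence has been judged and the etiology is unknown.

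None of these sets a date.

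**3. Next scheduled TBL**

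Chemistry panels in Table 3, without remote Weeks 8 and 16: Weeks 1, 4, 12, 20, 24, 30, 36, 42, 48, 52, then Week 53.

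| Trigger at week | 1 | 4 | 12 | 20 | 24 | 30 | 36 | 42 | 48 |
|---|---|---|---|---|---|---|---|---|---|
| Weeks to next panel | 3 | 8 | 8 | 4 | 6 | 6 | 6 | 6 | 4 |

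- Sorted: 3, 4, 4, 6, 6, 6, 6, 8, 8. The median is 6 weeks.
- Range: 3 x 7 = 21 days to 8 x 7 = 56 days, against 2-3 days for the repeat.
- Visits carry a window of ±3 days (Section 6.2), so a gap between two visits can move by up to 6 days either way: 21 - 6 = 15 to 56 + 6 = 62 days.
- After a trigger at Week 52, the next panel is at Week 53, 7-10 days later.
- In the active treatment phase, panels fall at Weeks 55, 58, 62, 66, 70, 74, 78, 84, 90, 96 and 102. The gaps are 3, 4, 4, 4, 4, 4, 6, 6, 6 and 6 weeks (median 4).

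**4. Illustration (assumed values)**

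TBL rises from 0.9 to 1.6 mg/dL, with ALT and AST unchanged.

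- Monitoring trigger: 1.5 x 0.9 = 1.35 mg/dL.
- Observed ratio: 1.6 / 0.9 = 1.78 x BLM, so the row opens.
- TBL limb of the discontinuation row: 2 x 0.9 = 1.80 mg/dL, not reached. That row also needs ALT or AST above 2 x BLM, so an isolated TBL rise of any size does not meet it.
- For assumed baselines of 0.5 to 1.2 mg/dL the trigger runs from 1.5 x 0.5 = 0.75 to 1.5 x 1.2 = 1.80 mg/dL. The mismatch is the same throughout.

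For context, 1.6 mg/dL exceeds the 1.3 mg/dL limit in exclusion criterion 30. That limit applies at screening, has an exception for Gilbert's syndrome, and is not an on-treatment action level.

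**5. Discontinuation row**

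Chemistry and PT/INR are scheduled together at the on-site visits from Week 1 to Week 52. The combined ALT/AST plus TBL or INR criterion can therefore be met on the triggering draw, and the omission does not affect it in the same way.

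**The case against.** The strongest reply is that this is an elliptical sentence, not a real gap. A bilirubin trigger still brings the subject back for a blood draw at 48-72 hours. The protocol defines a chemistry panel holding TBL, ALT and AST together, and describes no stand-alone ALT/AST assay. The cell goes on to mention TBL in the work-up and the exit rule, so a sensible investigator would measure it. A delay of weeks requires a site to recall a subject for raised bilirubin, leave bilirubin off the request, and then wait for the next visit. The medical monitor can ask for more tests, and both the sponsor's safety team (Section 9.9.2) and the data monitoring committee (Section 9.9.3) review safety data.

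Much of this stands. The practical gap is probably small, and the 21-56 days describe the scheduled-visit fallback, not an expected delay. No count of affected subjects is possible, and an isolated TBL rise would not stop treatment under the discontinuation row.

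It does not remove the point. Nothing says the repeat is a full panel, the medical-monitor clause and unscheduled visits are discretionary, and the two review bodies do not set a date for one subject's retest. That the row uses TBL before and after the repeat shows what was probably meant, but the sentence does not say it.

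**Conclusion.** The concern holds. For a TBL-only trigger in subjects with elevated ALT and/or AST at baseline, the written confirmation step does not fit its own trigger, and the work-up and weekly monitoring depend on that step. The defect is one of timing and confirmation.

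Its size is bounded. It affects only TBL-only entries, whose number the documents do not allow one to estimate. If scheduled visits alone were used, the recheck would come a nominal 3-8 weeks later up to Week 52 and 3-6 weeks later within the active treatment phase. This rests on reading the repeat as naming ALT and AST only and on no earlier discretionary testing. Sample size, power and type I error are not involved. The cell should be corrected, because a safety table should not rely on sites doing more than it states.

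**What to change.** In Appendix C, elevated-baseline monitoring row, change the first sentence of the action to: *Repeat ALT, AST and TBL within 48-72 hours.* Leave the thresholds, the weekly monitoring and the follow-up sentence as they are.

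The cost is one analyte in one table cell. TBL is on the same chemistry panel and the same draw, so no visit, tube or procedure is added.

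Two additions are optional. The first is to add TBL to the repeat in the normal-baseline row as well, because its discontinuation rule uses TBL and INR, although its trigger and repeat already agree. The second is to add INR to either repeat, which would need a separate coagulation sample.

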APPENDIX D. HEPATITIS EXCLUSION CRITERIA

Subjects who meet any of the Hepatitis B criteria described in the table below are ineligible for the study.

	Result	Interpretation
HBsAg anti-HBc IgM anti-HBc anti-HBs	Positive Positive Positive Negative	Acutely infected
HBsAg anti-HBc IgM anti-HBc anti-HBs	Positive Positive Negative Negative	Chronically infected
HBsAg anti-HBc anti-HBs	Negative Positive Positive	Immune due to natural infection*
HBsAg anti-HBc anti-HBs	Negative Positive Negative	Interpretation unclear; four possibilities*: 
 • Resolved infection (most common) • False-positive anti-HBc, thus susceptible • “Low level” chronic infection • Resolving acute infection

Abbreviations: HBsAg= hepatitis B surface antigen; anti- HBc= antibody to the hepatitis B core antigen; anti- HBs= antibody to hepatitis B surface antigen; IgM anti-HBc= IgM antibody to hepatitis B core antigen.

* Perform hepatitis B virus (HBV) deoxyribonucleic acid (DNA):

- If HBV DNA is **detected**, then participant must be excluded.
- If HBV DNA is **not detected**, then the participant may be considered eligible for enrollment based on the investigator’s judgment and after discussion with the study Medical Monitor.

Source: [Mast, 2005](#).

Celgene Signing Page

This is a representation of an electronic record that was signed electronically in Livelink.
This page is the manifestation of the electronic signature(s) used in compliance with
the organizations electronic signature policies and procedures.

UserName: [REDACTED]
Title: [REDACTED]
Date: Friday, 16 April 2021, 12:13 PM Eastern Daylight Time
Meaning: Approved, no changes necessary.
=====

1. JUSTIFICATION FOR AMENDMENT

Changes included in this amendment are summarized below:

- **100 mg dose treatment arm was removed**
 - [REDACTED]
 - [REDACTED] The subjects who are randomized to the 100 mg dose group prior to implementation of Protocol Amendment 4 will stay on 100 mg QD dose throughout the study.
 - Sections affected
Protocol Summary, Rationale (Section 1.3), Study objectives and Endpoints (Section 2), Overall Study Design (Section 3), Study Population (Section 4), Method of Treatment Assignment (Section 7.3), and Statistical Considerations (Section 9)
- **Stage 4 population was removed**
 - The protocol was revised to focus on assessing the efficacy and safety of CC-90001 in subjects with NASH and Stage 2 or Stage 3 liver fibrosis in this study.
 - Sections affected
Protocol Summary, Rationale (Section 1.3), Study objectives and Endpoints (Section 2), Overall Study Design (Section 3), Study Population (Section 4), Table of Events (Section 5), Procedures (Section 6), Method of Treatment Assignment (Section 7.3), Statistical Considerations (Section 9), and Appendix C
- **Active Treatment/Extension Phase was removed**
 - Active treatment/extension phase was removed to reduce burden for the subjects due to the Coronavirus Disease 2019 (COVID-19) pandemic and to shorten the duration of the study. Subjects who sign informed consent form (ICF) prior to the implementation of Protocol Amendment 4 will have an option to participate active treatment/extension phase.
 - Sections affected
Protocol Summary, Rationale (Section 1.3), Study objectives and Endpoints (Section 2), Overall Study Design (Section 3), Table of Events (Section 5), Procedures (Section 6), Method of Treatment Assignment (Section 7.3), and Statistical Considerations (Section 9)
- **Exclusion criterion #21 “Subjects has 2 positive fecal occult blood test (FOBT) during Screening, collected at least 4 weeks apart” was removed**
 - [REDACTED] Positive FOBT may be caused by different causes (such as rectal hemorrhage, ulcers, colitis, diverticulosis). The protocol has excluded the subjects with a history of

inflammatory bowel disease and the subjects with a history of bleeding peptic ulcer or bleeding diverticular disease within 5 years. Furthermore, the protocol also implemented FOBT at Screening and approximately every 12 weeks during the study and discontinuation criteria for the subject with positive FOBT in the study. With all these in place the occurrence of GI bleeding in the study continues to be well monitored to ensure safety of subjects over the course of the trial.

- Sections affected

Study Population (Section 4), Table of Events (Section 5), and Procedures – Screening Phase (Section 6.1)

- **Condition of worsening liver function was changed**

- The values of alanine aminotransferase (ALT)/ aspartate aminotransferase (AST) fluctuate over the short period of time as well as over the course of NASH disease. More than 20% increase of ALT or AST value in the subjects with ALT or AST less than 3 X upper limit of normal (ULN) may not be an evidence of worsening of liver function. In addition, throughout the study hepatotoxicity is monitored and subjects are to be discontinued if liver biochemistry abnormalities meet the discontinuation criteria (Appendix C). Therefore, the protocol was revised that another measurement is obtained, at least 4 weeks apart, only in the subjects with screening ALT or AST greater than 3 X ULN. If retested ALT or AST increase more than 20% the subject will be excluded from study.

- Sections affected

Procedures – Screening Phase (Section 6.1) and Appendix C

- **Approved weight-loss medications were removed from prohibited medications**

- Exclusion criterion #12 was removed and inclusion criterion # 6 was revised to allow anti-obesity medications in the study if the medications have been stable for 3 months prior to Screening or historical biopsy used for Screening.

- Sections affected

Study Population (Section 4) and Concomitant Medications and Procedures (Section 8)

- **Changed Visit 5 Week 8 and Visit 7 Week 16 to remote visit**

- Visit 5 Week 8 and Visit 7 Week 16 were changed to remote visit to reduce operational complexity and the burden for the subjects.

- Sections affected

Table of Events (Section 5) and Procedures (Section 6)

The amendment also includes other minor clarifications and corrections.

1. JUSTIFICATION FOR AMENDMENT

The primary purpose of this amendment is to expand the study population to allow inclusion of subjects with Non-alcoholic Steatohepatitis (NASH) and Stage 2 fibrosis. Modifications to inclusion/exclusion criteria were made to broaden the study population.

Changes included in this amendment are summarized below:

- Protocol Title (Title Page and Protocol Summary)
The title was changed to “A Phase 2, Randomized, Double-blind, Placebo-controlled, Multicenter, Dose-finding Study to Evaluate the Efficacy and Safety of CC-90001 in Subjects with Non-alcoholic Steatohepatitis (NASH) and Liver Fibrosis”
- Therapeutic Area Head signature page
 - Name and title of therapeutic area head was changed
- Protocol Summary, Rationale (Section 1.3), Study objectives and Endpoints (Section 2), Overall Study Design (Section 3), Study Population (Section 4), Method of Treatment Assignment (Section 7.3), Statistical Considerations (Section 9), [REDACTED] and Appendix C
 - Expanded study population to allow subjects with NASH and Stage 2 fibrosis in the study and evaluate efficacy and safety of CC-90001 in these subjects.
 - References to [REDACTED] Appendix C were removed from Study population, Table of Events footnote and Procedures sections because they did not apply to Stage 2 fibrosis. [REDACTED] Appendix C were removed as well.

- 
- Study Population (Section 4) Procedures (Section 6) and Concomitant Medications and Procedures (Section 8)
 - Inclusion criterion #6 was revised to clarify that this criterion applies to all fibric acid derivatives (fibrates) and to ensure that if sodium-glucose co-transporter 2 inhibitors and glucagon peptide-1 agonists have been discontinued those medications must have been stopped 3 months prior to screening or historical biopsy. The Permitted Concomitant Medications and Procedure (Section 8.1) was updated accordingly.

- Inclusion criterion #7 was revised to change stable dose of thiazolidinediones or vitamin E from 6 months to 3 months and to ensure that if thiazolidinediones or vitamin E have been discontinued those medications must have been stopped 3 months prior to screening or historical biopsy. The Permitted Concomitant Medications and Procedure (Section 8.1) was updated accordingly.
- Exclusion criterion #4 was revised to exclude subjects with HbA1C \geq 9.5%.
Protocol allows for dose initiation/adjustments on of anti-diabetic medications during the study in order to optimize clinical care and safety risk to the subjects with HbA1C < 9.5% is low.
- Exclusion criterion #5 was revised to clarify that worsening of liver function is based on aspartate aminotransferase, alanine aminotransferase, alkaline phosphatase and total bilirubin laboratory values.
- Exclusion criterion #7 was revised to remove bariatric surgery from this criterion
- Exclusion criterion #10 was revised to remove the drugs historically associated with nonalcoholic fatty liver disease (amiodarone, methotrexate, systemic glucocorticoids, tetracyclines, tamoxifen, estrogens at doses greater than those used for hormone replacement, anabolic steroids, valproic acid, and other known hepatotoxins) from this criterion. The Prohibited Concomitant Medications and Procedure (Section 8.2) was updated accordingly.
- Exclusion criterion #17 was revised to allow subjects with a history of hepatitis C virus (HCV) and sustained viral response (undetectable HCV ribonucleic acid [RNA]) for at least 2 years prior to Screening including negative HCV RNA at Screening.
- Exclusion criterion #23 was revised to allow subjects with a history of malignancy beyond 5 years to be enrolled in the study.

- Exclusion criterion # 30 was revised to “Prior use of obeticholic acid or participation of obeticholic acid clinical trial within 6 months prior to Screening or historical biopsy used for Screening”
 - Removed exclusion criterion #31
 - Added new exclusion criterion #31 to exclude subjects with history of bariatric surgery within 5 years prior to Screening or likely to have bariatric surgery during the study
 - Renumbered exclusion criteria #32 and #33 to align with the electronic case report form and updated criteria of serum total bilirubin.
- Protocol Summary, Rationale (Section 1.3), Study objectives and Endpoints (Section 2), Study Population (Section 4), Table of Events (Section 5) and Procedures (Section 6)

- Revised exclusion criterion #13 to clarify that subjects with SARS-CoV-2 infection within 4 weeks of Screening will be excluded and symptoms must have completely resolved
- Added exclusion criterion #34 to exclude subjects who have received live attenuated or investigational SARS-CoV-2 vaccine within 3 months prior to the first dose of study treatment.
- Clinical Laboratory Assessments (Section 6.5.3)
 - Changes were made to clarify that fasting is required for certain visits.
- Dose Interruptions (Section 7.2.2)
 - Revised to clarify that Investigational Product (IP) should be interrupted 7-10 days prior to an elective surgical procedure
- Concomitant Medications and Procedures (Section 8)
 - Use of cannabinoid products other than cannabis oils during the study was added to prohibited medication
 - Clarification and corrections were made to Permitted and Prohibited Concomitant Medications and Procedures
- Adverse Event (Section 10)
 - Clarification was made that only Serious Adverse Events occurring after first dose of IP will be reported to Celgene Drug Safety

- Appendix C: Hepatotoxicity Monitoring Criteria for Interruption and Discontinuation of Investigational Product Based on Liver Function Test Abnormalities
 - Clarifications were made in Appendix C
- Appendix D: Hepatitis Exclusion Criteria

The amendment also includes other minor clarifications and corrections.

